12.1 Analysis sets

The Full Analysis Set (FAS) comprises all participants who have signed the Informed Consent and who have received at least one dose of study treatment. The FAS will be used for the summary of demography and baseline characteristics as well as for all efficacy analyses.

The Safety Set (SAF) is identical to FAS in this study. The Safety Set will be used for all safety analyses.

12.2 Participant demographics and other baseline characteristics

Demographics, MS disease history, MRI baseline characteristics and MS medication history will be summarized descriptively and/or listed for the FAS as appropriate.

Categorical data will be presented as frequencies and percentages. For continuous data, mean, standard deviation, median, minimum, and maximum will be presented. For selected parameters, 25th and 75th percentiles will also be presented.

Relevant medical histories and current medical conditions at baseline will be summarized by system organ class and preferred term.

12.3 Treatments

The summary of exposure and time-at-risk will be based on the SAF.

Exposure to investigational study medication is defined as the number of days spent on study treatment divided by 365.25 days. Intermediate treatment interruptions will be subtracted from drug exposure. Exposure to investigational study medication will be summarized with number and percentage of participants by time category, and with summary statistics of the number of participant years of exposure. Further details will be included in the statistical analysis plan (SAP).

Time-at-risk is defined as the number of days spent in the study, from first dose to the last dose of study medication, plus the safety data cut-off of 100 days (or until EOS for participants continue with commercial ofatumumab immediately after EOS, or until last dose of study

medication plus 100 days or one day before switching to another DMT, whichever comes earlier, for participants who have such switch in the PT FU). Intermediate treatment interruptions will be included in time-at-risk calculations. Time-at-risk corresponds to the time window used for adverse event reporting and can serve as a denominator to safety (e.g. in exposure-adjusted incidence rates). Time-at-risk will be summarized in a similar way to exposure to investigational study medication. Further details will be specified in the SAP.

Concomitant medications and significant non-drug therapies prior to and after the start of the study treatment will be summarized and/or listed according to the Anatomical Therapeutic Chemical (ATC) classification system.

12.4 Analysis supporting primary objectives

12.4.1 Definition of primary endpoint(s)

The primary endpoint is the annualized relapse rate (ARR), which is defined as the average number of confirmed MS relapses in a year. In the primary analysis, the ARR is estimated based on the FAS which follows the intent-to-treat principle using a negative binomial model by including individual cumulative confirmed relapse counts as the response variable with participants' time in study as an offset variable.

Two variables are required for the calculation of the ARR (excluding covariates):

- The cumulative number of confirmed MS relapses by participant is the response variable in the negative binomial model. The confirmation based on EDSS will be derived as defined in [Section 8.3.1](#).
- The time-in-study by participant will be used as an offset variable to adjust for the various length participants have been observed and at-risk of a confirmed MS relapse in the study.

12.4.2 Statistical model, hypothesis, and method of analysis

In the primary analysis, the ARR will be estimated by a negative binomial regression model with log-link function, the cumulative number of confirmed MS relapses per participant as the response variable, number of relapses in the previous year (or two years) before enrollment, baseline EDSS, baseline age and baseline number of Gd-enhancing T1 lesions as continuous covariates. Natural log of time on study in years will be used as the offset variable to account for the varying lengths of participants' time in the study. The adjusted ARR (i.e., model-based estimate adjusted for covariates) and the corresponding 95% confidence interval will be obtained.

The primary analysis will be performed for FAS.

12.4.3 Handling of missing visits/censoring/discontinuation

For participants who withdraw early from the study, the number of relapses up to the study discontinuation will be used for the primary analysis. No imputation will be applied to the incomplete study duration.

The primary negative binomial regression model with an offset for the time in study adjusts for missing information (drop-out) under the assumption of non-informative drop-out, information is missing at random, and constant relapse rate over time.

12.4.4 Supportive analysis

The primary analysis will be repeated based on all reported MS relapses (rather than on only the confirmed ones) for FAS population.

A summary of ARR time-based and ARR participant-based will also be given. Time-based ARRs are calculated by taking the total number of relapses observed for all participants in FAS divided by the total number of days in study of those participants and multiplied by 365.25 days. Also, participant-based ARR is presented, where individual ARRs are computed and summarized over participants for FAS population. -For above ARR calculations, the analysis will consider confirmed relapses only.

Additional sensitivity analyses may be defined in the statistical analysis plan.

12.5 Analysis supporting secondary objectives

12.5.1 Efficacy and/or Pharmacodynamic endpoint(s)

The following MRI efficacy variables will be analyzed based on FAS:

- The analysis of the number of Gd-enhancing T1 lesions per MRI-scan will be done using a negative binomial regression model with log-link function. The total number of Gd-enhancing lesions (cumulative count of Gd-enhancing lesions across all the MRI-scans per participant) will be used as the response variable, using baseline age and baseline number of Gd-enhancing T1 lesions as continuous covariates. Natural log of the number of MRI-scans will serve as the offset variable to account for the varying lengths of participants' time in the study. The number of Gd-enhancing lesions per scan will be estimated and the corresponding 95% confidence interval will be obtained.
- The analysis of the annualized rate of new or enlarging T2 lesions will be done using a negative binomial regression model with log-link function. The number of new or enlarging T2 lesions on the last available MRI scan relative to baseline will be used as the response variable, using baseline age and baseline volume of T2 lesions as continuous covariates. Natural log of the time (in years) of the MRI-assessment from the baseline/Screening scan will serve as the offset variable to account for the varying lengths of participants' time in the study. The number of new or enlarging T2 lesions per year will be estimated and the corresponding 95% confidence interval will be obtained.
- Change from baseline in T2 lesion volume on MRI will be summarized by visit.

12.5.2 Safety endpoints

For all safety analyses, the safety set will be used. Unless explicitly stated otherwise, only data up to and including the safety cut-off of 100 days after permanent study treatment discontinuation or treatment completion (or EOS for participants continue with commercial ofatumumab immediately after EOS, or min(last dose of study medication + 100 days, date of switching to another DMT - 1) for participants who have such switch in the PT FU) will be

included in the analysis and data beyond this time point for a participant will be excluded from safety analysis.

The assessment of safety data will be primarily based on the frequency and percentage of adverse events (including death and non-fatal serious adverse events). Additional safety assessments such as laboratory tests, physical examination (including examination of skin), and vital signs will be analyzed. Clinically significant findings in these additional safety assessments will be reported as adverse events and analyzed as such. The detailed analyses of additional safety assessments will be defined in the SAP.

Adverse events

Treatment-emergent adverse events including serious adverse events and deaths will be summarized up to and including the safety cut-off.

The number (and percentage) of participants with treatment emergent adverse events (events started after the first dose of study medication or events present prior to start of treatment but increased in severity based on preferred term) will be summarized in the following ways:

- by primary system organ class and preferred term.
- by primary system organ class, preferred term and maximum severity.

Separate summaries will be provided for adverse events related to study treatment, death, serious adverse events, and other significant adverse events leading to interruption or discontinuation, if appropriate.

Specific risks of interest will be defined by combinations of adverse event and/or other relevant safety data (e.g. lab data). The number (and proportion) of participants fulfilling such risk definitions will be summarized.

A participant with multiple adverse events within a primary system organ class will only be counted once towards the total of the primary system organ class.

Given the flexible follow-up of the study, treatment-emergent adverse events will also be summarized by reporting exposure-adjusted incidence rates (assuming a Poisson-process for adverse events). This will be done for all treatment-emergent adverse events, and for serious treatment-emergent adverse events, by primary system organ class and preferred term.

Vital signs

Vital sign measurements and their change from baseline will be summarized with descriptive statistics (mean, median, standard deviation, min, max) by visit. The number and percentage of participants with clinically notable vital signs will be presented, if appropriate. The clinically notable definitions will be provided in SAP as needed.

Clinical laboratory evaluations

The summary of laboratory evaluations will be presented for 2 groups of laboratory tests: hematology and chemistry.

Laboratory measurements and their change from baseline will be summarized with descriptive statistics (mean, median, standard deviation, min, max) by visit. The number and percentage of participants with clinically notable vital signs will be presented, if appropriate. The clinically notable definitions will be provided in SAP as needed.

Other safety evaluations

All clinically significant safety findings based on additional safety evaluations (e.g. physical examination, urinalysis etc.) must be reported as adverse events on the appropriate eCRF. The statistical analysis of these findings will be done in the analysis of adverse events. Other safety data will be summarized or listed as appropriate.

12.7 Interim analyses

One interim analysis is planned in approximately Q1 2025, unless the final analysis will have already been completed. The efficacy and safety data (including summaries on key efficacy and safety endpoints) will be submitted to NMPA for local license renewal for Kesimpta.

12.8 Sample size calculation

12.8.1 Primary endpoint(s)

The ARR of Chinese RMS participants treated with ofatumumab is assumed based on the pivotal studies, COMB157G2301 and COMB157G2302. Since the participants are treated up to 12 months in the current study, the cumulative ARR from Month 0 to Month 12 from the pivotal studies is adopted:

	Ofatumumab 20mg	Teriflunomide 14mg
Cumulative ARR from Month 0 to Month 12 in COMB157G2301 & COMB157G2302	0.145	0.307

Under the assumption of a negative binomial distribution ($\sim NB(\mu, k)$) for the ARR, where μ is the true ARR which we assume to be 0.15 based on the reference above, and k is the dispersion parameter which we assume to be 0.82 based on historical trialdata in MS. For different sample sizes, the following can be calculated using normal approximation: the 95% lower and upper ranges of the estimated ARR (point estimate), and the probability of showing the ARR on ofatumumab is significantly lower than 0.30 (i.e. lower than the historical reference value for the ARR in patients treated with teriflunomide based on the COMB157G2301 & COMB157G2302 trial data)). Note that this probability is equivalent to the probability that the upper limit of 95% CI is lower than 0.3. The results are showed below.

μ (true ARR)	k	Sample size	95% lower range of estimated ARR	95% upper range of estimated ARR	Probability that the upper limit of 95% CI is lower than 0.30
0.15	0.82	60	0.05	0.25	80.8%
0.15	0.82	65	0.05	0.25	83.8%

μ (true ARR)	k	Sample size	95% lower range of estimated ARR	95% upper range of estimated ARR	Probability that the upper limit of 95% CI is lower than 0.30
0.15	0.82	70	0.05	0.25	86.4%
0.15	0.82	75	0.06	0.24	88.6%
0.15	0.82	80	0.06	0.24	90.5%
0.15	0.82	85	0.06	0.24	92.1%
0.15	0.82	90	0.07	0.23	93.4%

Based on the calculation, a sample with 85 participants will provide an estimated ARR in [0.06, 0.24] with 95% probability. In addition, with a probability of 92.1%, a sample with this size will also provide a 95% CI with upper limit lower than 0.30, i.e. it would be strongly suggestive of a higher efficacy of ofatumumab compared with the historical teriflunomide data. Therefore, a sample size of 85 completers is considered adequate. Allowing for a dropout rate of 15% (dropout rate was 10.3% in COMB157G2301 and 17.3% in COMB157G2302), the sample size for this study will be approximately 100 participants.

Sample size calculation was performed in nQuery 8, Version 8.4.1.0, Statistical Solutions Ltd.

13 Ethical considerations and administrative procedures

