Interim analysis will be performed at the planned time point with details defined in [Section 12.7](#).

There will be no hypothesis testing performed in this study. Data will be summarized descriptively. In general, categorical data will be presented as frequency and percentage; continuous data will be summarized by mean, standard deviation (SD), median, minimum, and maximum. For primary efficacy endpoints, the point estimate and confidence interval will be model-based. Additional analysis populations may be defined and sensitivity analyses may be conducted to evaluate the impact of COVID-19 pandemic.

Any data analysis carried out independently by the investigator should be submitted to Novartis before publication or presentation.

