### **2.5.2 Statistical hypothesis, model, and method of analysis**

In the primary analysis, the ARR will be estimated by a negative binomial regression model with log-link function, the cumulative number of confirmed MS relapses per subject as the response variable, number of relapses in previous year, baseline EDSS, baseline number of T1 Gd-enhancing lesions and baseline age as continuous covariates. Natural log of time on study in years will be used as the offset variable to account for the varying lengths of subjects' time in the study. The adjusted ARR (i.e., model-based estimate adjusted for covariates) and the corresponding 95% confidence interval will be obtained.

In case of non-convergence, continuous covariates may be removed from the regression model in the order of: baseline EDSS, number of relapses in the previous year, baseline age.

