## 5.4 Statistical models

### 5.4.1 Analysis supporting primary objective(s)

The SAS procedure GENMOD will be used to conduct the analysis on the negative binomial regression model. In GENMOD, the log of the dispersion parameter will be used (lognb) as an option in model statement. The natural log of time in year is used as an offset by specifying offset option in the model statement.

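### The 92.1% chance that the 95% CI upper limit is below 0.30 is correct for the planning approximation used, but not for a CI computed from trial data

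*Protocol*

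**What the plan says.** Protocol 12.8.1 and SAP 3.1 carry the same sample size text. They assume a true ARR of 0.15 and a negative binomial dispersion k of 0.82, and they compare with 0.30 as the historical teriflunomide value. The method is described only as follows: "For different sample sizes, the following can be calculated using normal approximation". The chance of showing an ARR significantly below 0.30 is tabulated for 60 to 90 participants, with this remark: "Note that this probability is equivalent to the probability that the upper limit of 95% CI is lower than 0.3". For 85 participants the text concludes that "with a probability of 92.1%, a sample with this size will also provide a 95% CI with upper limit lower than 0.30" and calls such a result strongly suggestive of higher efficacy than teriflunomide. That figure and the 95% range of the estimate, [0.06, 0.24], are the two reasons given for 85 completers. A 15% dropout allowance then gives 85/0.85 = 100.

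The analysis sections plan a different interval. The opening of Protocol section 12 says: "For primary efficacy endpoints, the point estimate and confidence interval will be model-based". In SAP 2.5.2, "the ARR will be estimated by a negative binomial regression model with log-link function". Protocol 12.4.2 enters the number of prior relapses, "baseline EDSS, baseline age and baseline number of Gd-enhancing T1 lesions as continuous covariates", with log time on study as offset. SAP 5.4.1 fits the model in GENMOD, with the dispersion parameter on the log scale. For participants who withdraw early, "the number of relapses up to the study discontinuation will be used for the primary analysis" (Protocol 12.4.3). Protocol section 12 also states that no hypothesis testing will be done.

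**The concern.** A reader will take 92.1% as the chance that the CI in the study report excludes 0.30 when the drug performs exactly as assumed. The sample size text names neither the scale of the interval nor the source of its SE, and nothing connects the figure to the regression model that will produce the reported CI.

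Both omissions matter. The SE of a relapse rate rises with the observed rate, so an interval computed from data is wider exactly when the estimate is unfavourable. A log-link interval is also asymmetric, with its longer arm pointing up towards 0.30. Both features lower the probability.

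At stake is the interpretation of a study done for a post-approval commitment and license renewal. On the stated figure, a CI reaching 0.30 would be about a 1-in-13 event (7.9%) under the planning assumptions. If the true chance is two to four times that, such a result would be misread as a surprise.

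**Working it through.** **Inputs.** From Protocol 12.8.1 and SAP 3.1: ARR 0.15, k = 0.82, reference 0.30, two-sided 95% CI (z = 1.96), n = 85 completers, 100 enrolled. Follow-up is one year, with 336 days as a second case because a study month is 28 days and the Month 12 visit is at day 336 (Protocol section 8 and Table 8-1).

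**Step 1: reproduce the plan's figure.** On the raw scale with the SE fixed at the assumed rate:

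- SE = sqrt((0.15 + 0.82 × 0.15²)/n) = sqrt(0.16845/85) = 0.0445
- Probability = Φ((0.30 − 0.15)/0.0445 − 1.96) = Φ(1.41) = 92.1%
- Range = 0.15 ± 1.96 × 0.0445 = 0.063 to 0.237

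For n = 60 to 90 in steps of 5, the formula gives 80.8, 83.8, 86.4, 88.6, 90.5, 92.1 and 93.4%, which is every row of the table.

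**Step 2: what the formula counts as success.** Any observed ARR up to 0.30 − 1.96 × 0.0445 = 0.213 qualifies. With data showing 0.213, the SE is sqrt((0.213 + 0.82 × 0.213²)/85) = 0.0543, and the raw-scale upper limit is 0.213 + 1.96 × 0.0543 = 0.319. On the log scale the SE is sqrt((1/0.213 + 0.82)/85) = 0.255, and the upper limit is 0.213 × exp(1.96 × 0.255) = 0.351. Neither is below 0.30.

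**Step 3: exact probabilities for an interval computed from data, k known, no covariates.** The total relapse count is negative binomial with size n/k and mean 0.15 × n × t. For each interval type I found the largest count whose upper limit is below 0.30 and summed the distribution up to it. At n = 85 and one year, the raw-scale upper limit is 0.287 at 16 relapses and 0.303 at 17. The log-scale Wald limit is 0.288 at 14 and 0.303 at 15.

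| Interval, n and follow-up | Largest qualifying count | Probability |
|---|---|---|
| Raw scale, SE from data, 85, 1 year | 16 | 84.0% |
| Raw scale, SE from data, 85, 336 days | 15 | 85.2% |
| Log-link Wald, 85, 1 year | 14 | 69.3% |
| Log-link likelihood ratio, 85, 1 year | 15 | 77.5% |
| Log-link Wald or likelihood ratio, 85, 336 days | 13 | 70.3% |
| Log-link Wald or likelihood ratio, 100, 1 year, no dropout | 18 | 80.7% |

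Counts are whole numbers, so the exact figures move in steps. For example, the Wald figure is 76.2% at n = 86.

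**Step 4: cross-checks for the log-link Wald interval at n = 85, no covariates.** The closed form at one year is Φ(ln 2/0.297 − 1.96) = 64.6%, with 0.297 = sqrt((1/0.15 + 0.82)/85). Simulation with k estimated (10,000 trials) gives 68.4% at one year and 63.6% at 336 days. At an observed ARR of 0.15 the Wald CI is 0.15 × exp(±1.96 × 0.297) = 0.084 to 0.268.

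**Step 5: four covariates.** The documents give no covariate effects, no CI type, and no rule for where the adjusted ARR is evaluated, so this step rests on assumed covariates. Simulations of 1,000 to 3,000 trials per scenario used normal or skewed non-prognostic covariates, or prognostic ones with a rate ratio of 1.3 per SD. The probability was 76 to 91% with the ARR evaluated at covariate means and 62 to 80% with predicted rates averaged over participants. In the normal-covariate scenarios, the median adjusted ARR at the means was about 0.11 to 0.12 against a true 0.15, which explains part of the higher figures.

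**The case against.** - **The figure is not wrong, and the approximation is disclosed.** This stands as far as it goes. Every row follows from the stated inputs, so a reader who inferred an arithmetic error would be mistaken. But only the words normal approximation are disclosed; the scale and the fixed SE are not.
- **The equivalence sentence is sound.** It can be read as saying that significance against 0.30 and a CI excluding 0.30 are the same event. Under the approximation they are. It would be tempting to call the sentence false, but the text does not force that reading. It needs a qualifier, not deletion.
- **69% is not the planned analysis either.** Correct. It is a Wald figure with k known, no covariates and completers only, and a likelihood-ratio interval gives 77.5%. A reader might infer that 69% is the true probability for this trial. The documents do not support any single figure for the four-covariate model.
- **Covariates could rescue it.** Possibly. All the covariate scenarios tried stayed below 92.1%, but stronger effects evaluated at the covariate means could exceed it. The adjusted ARR would then estimate a rate below the 0.15 that was planned for. A flat statement that 92.1% is optimistic for the primary analysis would go too far.
- **The inputs are conservative.** The tabulated pivotal values are 0.145 and 0.307. With these, the exact log-link Wald figure at n = 85 is 80.8% (one year) or 74.1% (336 days). But the plan's own formula also rises: SE = sqrt((0.145 + 0.82 × 0.145²)/85) = 0.0437, and Φ(0.162/0.0437 − 1.96) is about 96%. The gap remains.
- **Nothing is tested.** This stands, and it limits the consequence to the planning statement.

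**Conclusion.** The point holds in a limited form. The 92.1% is right for a raw-scale normal interval with its SE fixed at the assumed ARR, one year of follow-up and no covariates. It does not carry over to a CI computed from trial data. At ARR 0.15, k = 0.82 known, 85 completers and one year, the probability is 84.0% on the raw scale, and 69.3% (Wald) or 77.5% (likelihood ratio) for a log-link CI without covariates. At 336 days both log-link figures are 70.3%. With all 100 followed for a full year the log-link figure is 80.7%.

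That the planned CI is formed on the log scale and back-transformed is inferred from the log link; the documents do not say so. For the covariate-adjusted CI itself, the direction is likely downward but the size is open.

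A reader might also infer that the trial is too small. The documents do not support that: no success rule or test depends on the CI lying below 0.30, and the [0.06, 0.24] range is unaffected. The fault is an unsuitable planning approximation presented without its conditions.

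**What to change.** Keep the sample size and the [0.06, 0.24] range. Make three edits in both Protocol 12.8.1 and SAP 3.1:

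1. Label the last table column: *raw-scale normal approximation, SE fixed at the assumed ARR, 1 year of follow-up, no covariates*.
2. Keep the equivalence sentence and add: *The equivalence holds under this approximation; for a log-link model-based CI without covariates the probability is lower.*
3. Qualify the 92.1% as holding under this approximation, and add: *For a log-link CI without covariates, 85 completers followed for one year give 69.3% (Wald) to 77.5% (likelihood ratio), with k taken as 0.82. At an observed ARR of 0.15 the expected 95% Wald CI is about 0.08 to 0.27.*

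Alternatively, replace the column with a simulation of the planned log-link model, using 336-day follow-up and the expected dropout. State the CI type, the covariate assumptions, and whether the adjusted ARR is evaluated at covariate means or averaged over participants.

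The cost is a label and a few sentences in each document, or one simulation exercise. The only downside is a less favourable stated probability. No extra participants are needed and the analysis does not change.
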